#### Secondary endpoint

A sample of 20 patients in each Centre will be selected by the physician to be monitor using a new cutting-edge medical device working the telemedicine approach. A telehealth virtual office visit can be performed from the patient's home or workplace, decreasing time spent traveling to visit site, time spent in waiting room, and cost to patient. Studying telehealth may improve quality of life in patients during the therapy visit, especially in this SARS-CoV-2 pandemia.

### **Study Population**

Patients or health professionals already tested positive for the viral RNA from nasopharyngeal swabs by RT-PCR. Patients or health professional who are suspected of being infected with SARS-CoV-2 in the hospital. Patients who are considered at high risk for infection and eligible for active therapy and major surgery.

## Criteria

### **Inclusion Criteria:**

#### **1. Suspected cases**

Meet the following 2 at the same time:

a) Epidemiological history: There was a history of contact with confirmed cases before the onset of illness; or subjects with at least *one symptom* in the last week before accrual in the trial. Subjects that have been in contact with people positive for SARS-CoV-2 in the previous 14 days.

b) Clinical manifestations are defined as :

Fever >37.5°; dry cough, muscle aches and/or fatigue, anosmia, subjects with respiratory distress (Respiratory Rate >25/min or O2 Saturation <92%)

or imaging characteristics of pneumonia;

or the total number of white blood cells is normal or decreased with the lymphocyte count decreased in the early stage of onset or there is an abnormal C-Reactive protein. Other symptoms that clinical investigator will relate to SARS-CoV-2 infection.

Subject or cancer patients who have been quarantined for suspect symptoms and have access to hospital to continue therapy or to receive major surgery

#### **2. Confirmed cases**

Patients or subjects with positive RT-PCR for SARS-CoV-2. On the basis of meeting the criteria for suspected cases, sputum, throat swabs, lower respiratory tract secretions, and other specimens were tested by real-time RT-PCR for positive nucleic acid detection of new coronavirus; or viral gene sequencing was highly homologous with known new coronaviruses. Patients positive are serially tested with SARS-CoV-2 IgM / IgG Rapid Test to evaluate the immune response in IgG negative patients and the reliability of the test in those patients who develop clinical signs of SARS-CoV-2 during the trial.

3. Patients who are considered at high risk for infection and eligible for active therapy and major surgery

- Frailty (age and multiple comorbidities) planned to receive a standard systemic anticancer treatment comprising chemotherapy and/or immunotherapy and/or radiation therapy or to receive an experimental treatment
- Major surgery or surgery after neoadjuvant chemotherapy and or chemo/radiotherapy

### **Exclusion Criteria:**

1. Ascertained influenza virus, parainfluenza virus, adenovirus, respiratory syncytial virus, rhinovirus, human metapneumovirus, SARS coronavirus, and other known other viral pneumonia;

2. Ascertained mycoplasma pneumoniae, chlamydia pneumonia, and bacterial pneumonia; non-infectious diseases such as vasculitis, dermatomyositis, and organizing pneumonia.

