03 APR 2020

\_\_\_\_\_  
Date dd-MON-yyyy

Study Type: Observational

Estimated Enrollment: 1000 participants (200 per site)

Observational Model: Cohort

Time Perspective: Prospective

Timelines:

Actual Study Start Date: April 15, 2020

[figure not shown]
Estimated Primary Completion Date: July 31, 2020

Estimated Study Completion Date: December 31, 2020

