### **Aim of the study**

To validate in a real life study a self diagnostic assay for SARS-CoV-2 with the advantages of high speed, simple operation and low cost, and overcomes the shortcomings of the existing molecular detection methods. Clinical specimens from patients who were suspected of being infected with 2019-nCoV will be used to evaluate the performance of the assay. In parallel, we will also use molecular assays for the detection of the presence of the viral RNA from nasopharyngeal swabs since PCR is currently the gold standard.

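### Do the exclusions for other infections and inflammatory diseases undermine the specificity estimate of a real-life validation?

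*Combined protocol and SAP*

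**What the plan says.** The Aim of the study is "To validate in a real life study a self diagnostic assay for SARS-CoV-2", and it adds that "Clinical specimens from patients who were suspected of being infected with 2019-nCoV will be used to evaluate the performance of the assay". Study Population names three groups: people already confirmed by RT-PCR, "Patients or health professional who are suspected of being infected with SARS-CoV-2 in the hospital", and high-risk patients. No limit on other causes is stated there.

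Under Inclusion Criteria, the suspected-case definition joins an epidemiological history to findings that many respiratory illnesses share: fever, cough, aches, respiratory distress, "or imaging characteristics of pneumonia", or certain blood abnormalities. A further inclusion route requires no symptoms: "Patients who are considered at high risk for infection and eligible for active therapy and major surgery".

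The Exclusion Criteria have two items: "Ascertained influenza virus, parainfluenza virus, adenovirus, respiratory syncytial virus, rhinovirus, human metapneumovirus, SARS coronavirus, and other known other viral pneumonia" and "Ascertained mycoplasma pneumoniae, chlamydia pneumonia, and bacterial pneumonia; non-infectious diseases such as vasculitis, dermatomyositis, and organizing pneumonia". I read the word ascertained as governing both. No reason is given for either item, and no count of excluded people is requested.

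The Statistical Plan makes sensitivity and specificity the primary accuracy measures but does not name the population they describe. Performance study refers interference and cross-reactivity to the investigator brochure.

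**The concern.** Specificity depends on which negatives are tested. For a test meant for suspects, symptomatic people whose illness has another cause are an important group of negatives. Someone can meet the suspected-case definition in full and still be barred because, for example, influenza has been found. If the cassette reacts more often in such people, the reported specificity would be higher than users see in practice. The report would not show this, because the plan neither counts the excluded people nor limits the conclusion. Since no work-up for other causes is required, the group removed could also differ between sites with local testing habits.

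**Working it through.** **1. What the text removes.**

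- The suspected-case definition and the exclusions both stand under the heading Criteria, so they can be read as one definition of an eligible suspect. On that reading the Aim and the exclusions do not conflict; the claim is only somewhat narrower than the Aim's general wording.
- Only a listed condition that is already ascertained leads to exclusion. Undiagnosed cases enter, and nothing removes a subject whose other condition is found after enrolment.
- The exclusions make no exception for PCR-positive people. Co-infected confirmed cases are barred too, so sensitivity is restricted in the same way as specificity.

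**2. The plan's own specificity figures.** From the tables in Performance study, with exact (Clopper-Pearson) 95% intervals:

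- IgG: 49/50 = 98.0%, interval 89.35% to 99.95% (stated: 89.4% to 99.9%).
- IgM: 48/50 = 96.0%, interval 86.29% to 99.51% (stated: 86.3% to 99.5%).

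Both agree with the plan to within rounding.

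**3. Possible size of the effect.** The documents give neither the share removed nor the false-positive rate in those removed, so this is an illustration under assumptions.

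- r = specificity in those kept: 98% (IgG) or 96% (IgM), assumed equal in suspects and high-risk patients.
- w = share of suspects among PCR negatives: 25%, 50%, 100% (assumed).
- s = share of suspect negatives removed: 5%, 10%, 20% (assumed).
- e = w × s, from 0.25 × 0.05 = 1.25% to 1 × 0.20 = 20%.
- fp = false-positive rate in those removed (assumed).

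Specificity in the broader group = (1 − e) × r + e × (1 − fp), so

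gap = reported minus broader specificity = e × (fp − (1 − r)).

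Gap in percentage points, at e = 1.25% and at e = 20%:

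| fp | IgG (r = 98%) | IgM (r = 96%) |
|---|---|---|
| 0% | −0.03 and −0.4 | −0.05 and −0.8 |
| equal to 1 − r | 0 | 0 |
| 5% | 0.04 and 0.6 | 0.01 and 0.2 |
| 10% | 0.1 and 1.6 | 0.08 and 1.2 |
| 20% | 0.2 and 3.6 | 0.2 and 3.2 |

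**4. Against sampling error.** With an assumed 500 PCR negatives, the 95% half-width is:

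- IgG: 1.96 × √(0.98 × 0.02 / 500) = 1.2 points.
- IgM: 1.96 × √(0.96 × 0.04 / 500) = 1.7 points.

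The grid of 3 values of w, 3 of s and 5 of fp has 45 cells. The gap exceeds the half-width in 4 IgG cells and 1 IgM cell, all with e of at least 10% and fp of at least 10%.

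**5. How far the result depends on the assumptions.** If 30% of negatives were removed at fp = 20%, the gap would be 0.30 × (98 − 80) = 5.4 points for IgG and 0.30 × (96 − 80) = 4.8 for IgM. The figure therefore reflects the chosen range. The 500 and w are unsupported as well: Clinical considerations requires PCR for IgM positives and otherwise leaves it to clinical judgement in suspects, so the number and mix of verified negatives are unknown.

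**6. What lifting the exclusions would yield.** Of 500 negatives, 1.25% to 20% is about 6 to 100 people. Example exact 95% intervals for specificity in that subgroup:

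- 5/6: 35.9% to 99.6%
- 22/25: 68.8% to 97.5%
- 90/100: 82.4% to 95.1%

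**The case for a change.** The strongest case for a change does not need a proven bias. The Aim speaks of real life and of suspects without qualification, the exclusions take out some people who meet the suspect definition, and the Statistical Plan does not say whom its specificity describes. Symptom-free high-risk patients do not replace symptomatic negatives with another diagnosis. A small overall gap also says nothing about performance within the excluded group. Across the five sites implied by 1000 participants at 200 each, local testing decides who is barred. Keeping a count and adding one limiting sentence would cost almost nothing.

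Much of this stands as description: the estimate is narrower than the Aim's wording, and if nobody counts the exclusions their number will not be recoverable. It does not amount to a fault in the plan. The exclusions are printed, so a reader can see whom the estimate covers. The limiting sentence needs care. To say that the results hold for subjects without another identified cause would misdescribe the cohort, because conditions found after entry and conditions not listed remain in. The accurate statement is that both sensitivity and specificity describe subjects without a listed condition ascertained at entry. An analyst can write that from the criteria as they are, and screening counts are a normal part of an accuracy report.

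Opening eligibility instead has a real price. It would create one eligibility rule for the accuracy endpoint and another for the rest of the cohort. It would also admit conditions that could plausibly confound the inflammation and immunity markers in the third primary endpoint. The plan does not give that as its reason, but it is a sensible one.

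**Conclusion.** No change to the plan is called for. The exclusions narrow the population for both accuracy measures, but they are openly stated, they act only on conditions already ascertained at entry, and they are a fair trade-off in a cohort that also studies inflammatory markers. No bias is shown. Its size and direction cannot be determined from the documents and may be zero.

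Under the main assumed ranges, the gap runs from −0.4 to 3.6 points for IgG and from −0.8 to 3.2 for IgM, and it is within sampling error in 41 of 45 and 44 of 45 scenarios. These results rest on the tabulated specificities, on assumed shares and false-positive rates, and on an assumed 500 verified negatives; a larger assumed share would give a larger gap. Admitting the excluded people might add as few as 6 negatives, too few to tell how the test performs in them. What remains is a matter of describing the population correctly when the results are reported.

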## Clinical considerations

All patients with epidemiologic history and/or clinical manifestations suspected for COVID will be proposed, according to the clinical judgement, for RT-PCR test for positive nucleic acid detection, irrespective of serological evidence.

All patients tested as IgM positive will have a confirmatory real-time RT-PCR test for positive nucleic acid detection of new coronavirus on sputum, throat swabs, lower respiratory tract secretions, and other specimens.

The 2019-nCov IgG/IgM Rapid Test Cassette (Whole Blood/Serum/Plasma) will be repeated in patients IgM positive for confirming the subsequent IgG positivity.

The tests will be performed locally in each hospital laboratory.

The ASST of Cremona laboratory could perform:

- [name], UO Laboratorio Analisi – ASST di Cremona: SARS-CoV-2 IgG/IgM Rapid Test Cassette (Whole Blood/Serum/Plasma) also for other sites. 1 ml of plasma will be needed;
- [name] SMeL849 – ASST di Cremona: *multiplex* immunoassay protein quantitation related to markers of inflammation and immunity (IL-6, TNF, INF $\gamma$ , IL1, IL-2, ect). 2.5 ml of plasma will be needed.

The lab responsible person in Milano IEO is:

Dr.ssa [name]  
Divisione di Medicina di Laboratorio  
Istituto Europeo di Oncologia

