#### Primary endpoints

- 1) To estimate the rate of SARS-CoV-2 positive cancer patients (undergoing chemotherapy, immunotherapy, biological therapy, radiotherapy or experimental treatments or major surgery) and health professionals in a comprehensive cancer center or in a cancer setting. Patients positive are serially tested with SARS-CoV-2 IgM / IgG Rapid Test to evaluate the immune response in IgG negative patients and the reliability of the test in those patients who develop clinical signs of SARS-CoV-2 during the trial.
- 2) To validate the accuracy of self diagnostic assay by confirmation of IgM and/or IgG positive test with the current gold standard RT-PCR for positive nucleic acid detection of new coronavirus from nasopharyngeal swabs.
- 3) To perform on plasma samples multiplex immunoassay protein quantitation related to markers of inflammation and immunity (IL-6, TNF, INF $\gamma$ , IL1, IL-2). 2.5 ml of plasma will be needed.

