## Statistical Plan

All data recorded will be summarized in tables, graphs and listings. In general, categorical data will be presented using counts and percentages, whilst continuous variables will be presented using the mean, standard deviation, median, minimum, maximum and number of patients.

In tabulations, denominators for calculation of percentages will be taken as the number of non-missing responses.

Primary end-point, the accuracy of tests, will be sensitivity and specificity and they will be calculated for all tests and compared with the appropriate statistical test.

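### RT-PCR verification depends on the rapid-test result and the plan does not correct for it; in a verified-only analysis with incomplete swabbing, IgM sensitivity is too high and specificity too low, while the direction for IgG is undetermined.

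*Combined protocol and SAP*

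**What the plan says.** Accuracy against RT-PCR is a primary endpoint. The Statistical Plan says the measures "will be sensitivity and specificity and they will be calculated for all tests". Five places bear on who receives the reference test and who is analysed:

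- Aim of the study: "Clinical specimens from patients who were suspected of being infected with 2019-nCoV will be used to evaluate the performance of the assay", followed by "In parallel, we will also use molecular assays for the detection of the presence of the viral RNA from nasopharyngeal swabs".
- Primary endpoints, item 2: accuracy is to be validated "by confirmation of IgM and/or IgG positive test with the current gold standard RT-PCR".
- Clinical considerations: "All patients tested as IgM positive will have a confirmatory real-time RT-PCR test for positive nucleic acid detection of new coronavirus". Patients with an epidemiological history or clinical manifestations "will be proposed, according to the clinical judgement, for RT-PCR test for positive nucleic acid detection, irrespective of serological evidence".
- Inclusion Criteria: confirmed cases (item 2) are "Patients or subjects with positive RT-PCR for SARS-CoV-2", so their reference result is known at entry. High-risk patients (item 3) may enter without being suspected. If they are IgM-negative, no section gives an RT-PCR rule for them.
- Statistical Plan: in tabulations, "denominators for calculation of percentages will be taken as the number of non-missing responses". There is no other rule on missing reference results, no accuracy analysis set and no method for verification bias.

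**The concern.** Under these rules the chance of having a reference result depends on the result of the test under evaluation. IgM-positives are always verified. IgM-negatives are verified only at clinical discretion or, in the non-suspected high-risk group, under no rule at all. IgG-only positives are a further gap: the endpoint speaks of confirming IgM and/or IgG positives, but the mandatory swab follows IgM alone.

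If the accuracy table is built from participants with both results, false negatives and true negatives are under-represented relative to true and false positives. For IgM this flatters sensitivity, so missed infections are understated, and it penalises specificity. Enrolling more participants does not reduce the error, and an ordinary confidence interval does not reveal it. If RT-PCR status and the reasons for swabbing are not recorded, the error cannot be repaired later.

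**Working it through.** **Inputs from the documents.** Performance study, Table 2 (IgM against PCR): 17 of 20 positives and 48 of 50 negatives correct. Recomputed with exact 95% intervals, this is 85.0% (62.1 to 96.8) and 96.0% (86.3 to 99.5), matching the stated figures. They are used below as illustrative true values, Se = 0.85 and Sp = 0.96. The verified fraction among IgM-positives is 1 (Clinical considerations).

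**Assumed inputs.** The documents give neither swab uptake among IgM-negatives nor prevalence nor group mix.

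**Step 1: direction for IgM.** Let u1 and u0 be the verified shares of infected and uninfected suspected IgM-negatives. In a verified-only table:

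- apparent Se = Se / (Se + (1 − Se)·u1)
- apparent Sp = Sp·u0 / (Sp·u0 + 1 − Sp)

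Any u1 below 1 raises sensitivity and any u0 below 1 lowers specificity, however clinical judgement selects patients. Prevalence and group size do not enter.

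**Step 2: size for IgM, suspected patients only, u1 = u0 = u.**

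| Uptake u | Sensitivity | Specificity | Error (points) |
|---|---|---|---|
| 100% | 85.0% | 96.0% | none |
| 90% | 0.85/0.985 = 86.3% | 0.864/0.904 = 95.6% | +1.3 / −0.4 |
| 70% | 0.85/0.955 = 89.0% | 0.672/0.712 = 94.4% | +4.0 / −1.6 |
| 40% | 0.85/0.910 = 93.4% | 0.384/0.424 = 90.6% | +8.4 / −5.4 |

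**Step 3: effect of pooling confirmed cases.** Assume 400 suspected patients, 30% infected (TP 102, FN 18, FP 11.2, TN 268.8), plus 100 confirmed cases (TP 85, FN 15). At 70% uptake, 12.6 of the 18 suspected false negatives are verified, so pooled sensitivity is 187/(187 + 15 + 12.6) = 87.1%, against 89.0% in suspected patients alone. At 90% and 40% it is 85.7% and 89.4%. The pooled figure therefore depends on a mix that the plan does not state. Sensitivity within the confirmed cases alone is untouched by this mechanism.

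**Step 4: bounds.** Of the 286.8 suspected IgM-negatives, 30% (86.0) are unverified at 70% uptake. Assigning them all to PCR-positive gives sensitivity 102/(102 + 12.6 + 86.0) = 50.8%; assigning them all to PCR-negative gives 89.0%. At 40% uptake the range is 36.3% to 93.4%.

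**Step 5: IgG.** Suppose all IgM-positives and half of IgM-negatives are verified. With assumed patterns among infected people (both lines, IgG only, IgM only, neither), verified-only IgG sensitivity is (both + 0.5·IgG only) / (both + IgM only + 0.5·(IgG only + neither)):

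- 0.80, 0.05, 0.05, 0.10: true 85.0%, observed 0.825/0.925 = 89.2%
- 0.55, 0.30, 0.10, 0.05: true 85.0%, observed 0.700/0.825 = 84.8%
- 0.40, 0.20, 0.35, 0.05: true 60.0%, observed 0.500/0.875 = 57.1%

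The sign changes with the joint pattern.

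**Step 6: what a correction achieves.** If verification depends only on the IgM result, the Begg-Greenes estimator returns 85.0%/96.0%. If instead 90% of infected and 60% of uninfected IgM-negatives are swabbed (400 suspected, 30% infected), verified FN = 16.2 and TN = 161.3, and the verified-only result is 86.3%/93.5%. Correction by test result alone assigns 286.8 × 16.2/177.5 = 26.2 false negatives, giving sensitivity 102/128.2 = 79.6% and specificity 260.6/271.8 = 95.9%.

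**The case against.** The strongest reply is that the Aim section promises molecular assays in parallel with the rapid test, which can be read as RT-PCR in every suspected patient, and that the swab offer is made whatever the serology shows. On that reading there is no bias among suspected patients. The reading is possible, but the Aim does not say that every participant is swabbed. A separate mandate for IgM-positives would add little for suspected patients if it did, and an offer subject to judgement is not universal. At best the sections conflict.

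Second, the non-missing denominator is stated for tabulations, and applying it to the two-by-two table is an inference. That is fair, but it is the only relevant rule given. If unverified IgM-negatives were instead counted as PCR-negative, sensitivity would be inflated just as much (91.9% at 50% uptake) while specificity would move slightly up (96.1% at 30% infected).

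Third, a reader might infer that the plan must bias every accuracy figure, with sensitivity up and specificity down. The documents do not support that. The direction is shown only for IgM, in a verified-only table, with uptake below 100%. It is not fixed for IgG and does not arise for sensitivity in cases confirmed at entry. Nor do the documents show that the error is large: at 90% uptake it is about one point or less.

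**Conclusion.** The concern holds in conditional form. Verification is tied to the IgM result, the accuracy set is undefined, IgG-only positives and non-suspected high-risk IgM-negatives may go unverified, and no handling is planned. For IgM, a verified-only analysis overstates sensitivity and understates specificity whenever some suspected IgM-negatives lack RT-PCR. Over assumed uptakes of 90% to 40% the error is +1.3 to +8.4 points for sensitivity and −0.4 to −5.4 points for specificity, and it is zero at 100%. These sizes rest on Table 2 as truth and on uptake values that the documents do not give; they illustrate the mechanism and do not predict this trial's results. Because a primary endpoint is affected and the remedy lies mainly in the analysis, it should be settled before the data are analysed.

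**What to change.** In the Statistical Plan:

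1. Make the suspected group, which the Aim names, the primary accuracy set. Report sensitivity in cases confirmed at entry separately, and do not pool the two into one headline figure.
2. For IgM, IgG and either-line positivity, tabulate verified and unverified counts by joint IgM/IgG pattern and inclusion group.
3. In the suspected group, replace the verified-only estimate with a Begg-Greenes, inverse-probability-of-verification or multiple-imputation estimate. Condition on the joint IgM/IgG result and on recorded variables likely to drive swabbing: contact history, type and severity of manifestation, imaging or laboratory findings, and site. Mere presence of symptoms is a weak stratifier, because the suspected-case criteria require history and manifestations together. Always report best- and worst-case bounds for unverified participants.
4. For high-risk participants who are not suspected, report positivity and the positive predictive value of verified positives only. Make no sensitivity or specificity claim there unless their test-negatives are verified.
5. Reconcile the Aim, Primary endpoints, Clinical considerations and Statistical Plan on who has the reference RT-PCR and who enters the accuracy analysis, including IgG-only positives.

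The cost is plan wording, extra analysis, and recording for every participant whether RT-PCR was done together with the variables in item 3. The analysis set becomes smaller and the intervals wider. The correction is valid only if verification depends on recorded variables; step 6 shows the error when it does not, so the bounds must accompany it even though they are wide.

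### Confirmatory RT-PCR is mandated for IgM positives only, narrower than the accuracy endpoint, and no rule covers participants without RT-PCR in sensitivity and specificity

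*Combined protocol and SAP*

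**What the plan says.** All references are to the combined protocol and SAP.

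- **Primary endpoints, item 2.** Accuracy is validated by "confirmation of IgM and/or IgG positive test with the current gold standard RT-PCR", on nasopharyngeal swabs.
- **Clinical considerations.** The compulsory step is narrower: "All patients tested as IgM positive will have a confirmatory real-time RT-PCR test". Patients with a suspicious history or symptoms "will be proposed, according to the clinical judgement, for RT-PCR test for positive nucleic acid detection, irrespective of serological evidence".
- **Inclusion Criteria, category 3.** The study also enrols "Patients who are considered at high risk for infection and eligible for active therapy and major surgery". Clinical considerations gives them no RT-PCR unless they are suspected or IgM positive. Confirmed cases (category 2) enter with a positive RT-PCR, so the gap does not concern them.
- **Aim of the study.** "Clinical specimens from patients who were suspected of being infected with 2019-nCoV will be used to evaluate the performance of the assay". The next sentence adds: "In parallel, we will also use molecular assays for the detection of the presence of the viral RNA from nasopharyngeal swabs". No schedule or per-participant rule follows.
- **Statistical Plan.** The accuracy endpoint is "sensitivity and specificity and they will be calculated for all tests". The only rule touching missing data is that, in tabulations, "denominators for calculation of percentages will be taken as the number of non-missing responses". Nothing separates RT-PCRs ordered on clinical grounds from those ordered because the cassette was positive.

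**The concern.** An IgG line without an IgM line is a defined cassette result (Interpretation of the results). A site that follows Clinical considerations alone would leave such results unconfirmed. A site that works from the endpoint would swab them. The two sites would then collect different data for the same primary endpoint.

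The second problem is partial verification. Where a positive IgM line guarantees the reference test and a negative one does not, the participants with an RT-PCR are enriched for IgM positives. Counting only those participants loses some false negatives, which raises apparent sensitivity. It also loses some true negatives, which lowers apparent specificity. These two measures are the stated accuracy endpoint.

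**Working it through.** **Inputs.** The plan gives no figure for this point to reproduce: the enrolment of 1000 has no derivation, and neither RT-PCR uptake nor the size of the high-risk group is stated. IgM performance comes from the Performance study, Table 2: sensitivity 17/20 = 85%, specificity 48/50 = 96%. Exact (Clopper–Pearson) intervals reproduce the printed 62.1%–96.8% and 86.3%–99.5%. These values are taken as true below; every other input is an assumption.

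**1. Suspected patients only.** Let a proportion s have RT-PCR on clinical judgement and the rest only if IgM positive.

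- Apparent sensitivity = 0.85 / [s + 0.85(1 − s)]
- Apparent specificity = 0.96s / [s + 0.04(1 − s)]

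| s | Sensitivity | Specificity |
|---|---|---|
| 100% | 85.0% | 96.0% |
| 90% | 0.85/0.985 = 86.3% | 0.864/0.904 = 95.6% |
| 70% | 0.85/0.955 = 89.0% | 0.672/0.712 = 94.4% |
| 50% | 0.85/0.925 = 91.9% | 0.48/0.52 = 92.3% |

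**2. Pooling unsuspected high-risk patients.** Let them be a share f of participants, with PCR prevalence p and RT-PCR only when IgM positive. Everyone else has RT-PCR, with prevalence q. Put D = (1 − f)q, H = (1 − f)(1 − q), TP = 0.85fp and FP = 0.04f(1 − p).

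- Pooled sensitivity = (0.85D + TP)/(D + TP)
- Pooled specificity = 0.96H/(H + FP)

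Example per 1000 with f = 0.5, p = 0.05, q = 0.5: D = H = 250, TP = 21.25, FP = 19. Sensitivity is 233.75/271.25 = 86.2% and specificity 240/269 = 89.2%.

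Ranges over p = 1% to 10% and q = 30% to 70%:

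| f | Sensitivity | Specificity |
|---|---|---|
| 10% | 85.0%–85.5% | 94.6%–95.5% |
| 25% | 85.1%–86.3% | 92.0%–94.4% |
| 50% | 85.2%–88.3% | 84.8%–91.3% |

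**3. Does widening the trigger to either line remove the bias?** No. In the pooled setting, sensitivity returns to 85% if every IgM-negative PCR positive shows an IgG line (IgG sensitivity was 20/20 in Table 1). For specificity, the wider trigger adds f(1 − p)r true negatives, where r is the IgG-only rate among PCR negatives. At f = 50%:

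- r from 0 to 2% (2% is Table 1's 1/50): 84.8% to 91.5%.
- r = 10.6% (exact upper limit for 1/50), worst case p = 1%, q = 70%: (0.144 + 0.0525)/(0.1698 + 0.0525) = 88.4%.
- r = 19.5% (10.6% false positives plus 10% past infection): worst case (0.144 + 0.0965)/(0.1698 + 0.0965) = 90.3%; best case (p = 10%, q = 30%) (0.336 + 0.0878)/(0.368 + 0.0878) = 93.0%.

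All stay below 96%, because participants negative on both lines remain unverified.

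For a positive result on either line, widening makes specificity slightly worse. Assume the lines are independent given PCR status, so true specificity is 0.96 × 0.98 = 94.1%. With 50% uptake among those not triggered, apparent specificity is 0.4704/0.5200 = 90.5% under the IgM trigger and 0.4704/0.5296 = 88.8% under the wider one.

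**4. Does excluding cassette-triggered RT-PCRs remove it?** Yes in this model (85% and 96% for any f or s), but only if the reason is coded correctly. If 30% of IgM positives who would have been swabbed anyway are coded as triggered and dropped, sensitivity is 0.595/(0.595 + 0.15) = 79.9% and specificity 0.96/(0.96 + 0.028) = 97.2%. The cassette reads in 10 minutes and the plan does not order it relative to the swab decision, so this error is plausible.

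**The case against.** Four stronger readings are tempting, and the documents do not support them.

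- **That the plan leaves IgG-only patients unswabbed.** The endpoint itself is defined by confirming either line, and Clinical considerations never excludes IgG-only patients. A site that swabs every positive satisfies both sections. What stands is that the compulsory instruction is narrower than the endpoint.
- **That the Statistical Plan pools all entry categories.** Its phrase about all tests is followed by a comparison between them, so it more naturally refers to assays. The non-missing rule is written for tabulations. The pooled figures are therefore conditional. What stands is that no other rule is given for participants without RT-PCR.
- **That bias is certain.** The Aim can be read as swabbing every suspected patient in parallel and limiting accuracy to them; the bias is then zero. However, the compulsory IgM trigger and the clinical-judgement wording would be redundant for suspected patients if all were swabbed.
- **That IgM sensitivity is 100% and specificity 0% by construction in high-risk patients.** This needs no other RT-PCR at all in that group, which the documents do not say.

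It is also fair that the shifts are often small. At a 10% or 25% high-risk share, specificity moves by at most 4.0 points and sensitivity by at most 1.3, well inside the Performance study's intervals. Those intervals come from 20 PCR-positive and 50 PCR-negative specimens, though, and a larger sample would not remove this bias.

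**Conclusion.** The point holds in a limited form. The compulsory RT-PCR rule is narrower than primary endpoint 2, and the plan has no rule for participants without the reference test. If accuracy is computed on whoever has an RT-PCR, IgM sensitivity is biased upward and specificity downward.

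The size cannot be fixed from the documents. In suspected patients it runs from nothing at full uptake to about +7 points in sensitivity and −4 in specificity at 50% uptake. Pooling unsuspected high-risk patients falls mainly on specificity: under 2 points at a 10% share, about 5 to 11 at 50%. These figures assume that the Performance study's IgM values are true, that clinical ordering does not depend on the cassette, and the prevalence ranges stated above.

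It is worth correcting because a primary endpoint is affected, the change is cheap, and the reason for an RT-PCR is best recorded when it is ordered.

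**What to change.** 1. In Clinical considerations, make confirmatory RT-PCR compulsory after a positive IgM line, IgG line or both, to match endpoint 2. This alone does not remove the bias.
2. Record the clinical decision on RT-PCR (already confirmed, clinically suspected, or not indicated) before the cassette is read. Class any RT-PCR with a clinical indication as clinical, even if the cassette is also positive.
3. Base primary sensitivity and specificity on confirmed cases and on suspected patients whose RT-PCR was clinically indicated. Exclude RT-PCRs done solely because of the cassette.
4. For cassette-triggered RT-PCRs report only the share confirmed, for IgM-only, IgG-only and double-positive results and by entry category, with the number lacking RT-PCR.

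**Cost.** One amended sentence, one recorded field, one table and a smaller accuracy set, plus added swabs for IgG-only results. Assume 5% of unsuspected high-risk patients are PCR positive and 15% of those are IgG-only (3/20, if Tables 1 and 2 share specimens, which is not stated). At 2% IgG false positives, 0.95 × 2 + 5 × 0.15 = 2.65 swabs per 100 such patients; at 10.6%, 0.95 × 10.6 + 0.75 = 10.8. If 10% of PCR-negative patients had past infection and all were IgG positive, the figure per 100 PCR negatives is 100 × (0.10 + 0.90 × 0.02) = 11.8 to 100 × (0.10 + 0.90 × 0.106) = 19.5. The false-positive and past-infection parts include patients who also have an IgM line and are already swabbed, so they overstate the addition. Suspected IgG-only patients not otherwise swabbed would add a number that the documents do not allow one to estimate.
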